18.1.4 Duloxetine

Predictors of response in light phenotyping (Aim 2). We have several *a priori* hypotheses regarding the PROs that will identify a subset of cLBP patients who will preferentially respond to duloxetine, or another similar SNRI. We hypothesize that we will replicate previous studies suggesting that cLBP participants will preferentially respond to this therapy if PROs indicate *stronger elements of either neuropathic pain (indicated by a high PainDETECT score^{140,141}) or centralized/nociplastic pain (indicated by more widespread pain on the FSQ¹³⁵).*

Predictors of response in deep phenotyping (Aim 3). We and others have also performed QST and/or neuroimaging studies that suggest that the subgroup of cLBP patients with either neuropathic or centralized/nociplastic pain will preferentially respond to SNRIs. Yarnitsky et al. showed that the subset of neuropathic pain patients with diminished endogenous pain inhibition, measured using a conditioned pain modulation (CPM) procedure,¹⁴² were more likely to respond to duloxetine. Our group has performed a series of studies with a different SNRI, milnacipran, and showed that the drug preferentially works in individuals with a brain imaging pattern consistent with decreased descending analgesia, namely decreased connectivity between the periaqueductal gray (PAG) and the insular cortex, as well as between the rostral part of the anterior cingulate cortex and the insular cortex.¹⁴³ We have shown that the stimulated inflammatory response (i.e., inflammation after LPS-stimulation) is strongly associated with centralized pain characteristics such as multifocal pain and the number of pain syndromes present in the MAPP study.^{144,145} This appears to be true in MAPP patients with cLBP as well (see NPC preliminary data). We anticipate then that *deficient pain inhibition* on QST, *decreased PAG-insula connectivity*, and *elevated stimulated inflammatory responses* will be associated with a positive response to centrally-acting duloxetine.

18.1.5 Descriptive statistics

We will use descriptive statistics to assess data quality and characterize relationships between phenotype features prior to each treatment. In preparation for the main multivariate model-based analysis we will look at correlations between phenotype variables and responses with correlation analysis and scatterplots, analyze data for evidence of (near) collinearity between factors, study patterns of missing data, and conduct univariate analysis using models described below. The goal of this analysis is to elicit a good feel for the specific data in our team of analysts and to guide an initial approach to data reduction and predictive model trimming. Another round of descriptive model-based analysis will occur after the multivariate model-based data analysis to assess the adequacy of proposed models with model diagnostic plots and other tools.

Longitudinal data analysis. For hypothesis testing, we will use model-based likelihood ratio tests. The main hypotheses of differential treatment effects (treatment moderators, treatment effect modifiers) will be handled by introduction of the interaction terms between the phenotype and treatment indicator variables. We will base longitudinal analysis on multivariate linear and logistic mixed models with choice appropriate to the type of response variable (Logistic regression with yes/no type variables; the Proportional Odds Cumulative Logit for modeling ordinal responses; linear model and generalized linear model with continuous quantitative scores). Gaussian subject-specific intercept term will be used to model the effect of unmeasured factors shared by longitudinal observations on the same subject. While the continuous form of analgesic and secondary endpoint variables will be used in the primary line of analysis, for robustness and to gain insight into a need for specific link functions and variable transformations, we will also use binary (clinically relevant 30% and 50% improvement in analgesic responses [yes/no]) as well as ordinal form of the responses.

Best model selection. We will select best models using the unbiased Bayesian Information Criterion (BIC) and use 10-fold cross-validation to protect against overfitting the model. To deal with potentially high-dimensional phenotype variables and other demographic and clinical covariates, regularized regressions will be considered. Penalties in the likelihood function will follow the Elastic Nets family with LASSO favored for its feature elimination potential. Alternative machine-learning model-free algorithms (random forests, SVMs) will be utilized for comparison, using the binary form of the response variables.

Characterizing the predictive performance. Cross-validated and BIC-based measures of explained variation will be used to characterize the predictive potential of the continuous response models. This analysis will be supplemented with ROC analysis based on the binary form of the response variables. We will use the cross-validated and kernel-smoothed area under the ROC curve (AUC) as an appealing measure of the predictive potential with good interpretability. Order effects will be considered during secondary analysis.

Causal analysis. We will conduct exploratory analysis of causal relationships between the light and deep phenotypic factors and the analgesic and secondary response variables. We are interested in particular causal analyses potentially implicating neurobiological and inflammatory biomarkers (deep phenotyping variables) as having a mechanistic role in the mediation of the treatment effects of light phenotypic measures. Specifically, we will measure the potential mediation effect of the deep phenotype biomarkers as the proportion of the treatment effect (PTE) explained by the biomarker. PTE is represented by a relative change in the treatment regression coefficients when the biomarker is included in the model relative to the coefficient before inclusion. We will use bootstrap methods to estimate standard errors for the proportion of explained treatment effects. Wald test statistic of the form (change in regression coefficient)/(bootstrap Standard Error) will be used to test for the presence of the mediation effect.

Handling of non-study interventional procedures. Interventional procedures are different from the 4 main study treatments in that they are not subject to randomization controlled by the SMART trial and thus carry a risk of bias due to confounding by indication. We will develop causal models to deal with these effects and reduce the bias associated with these treatments to the extent possible. Interventional procedures represent dynamic treatment regimen whose initiation decision is adapted to the dynamically accumulating patient symptoms. In this situation, naïve application and interpretation of regression models correlating treatments with outcomes are misleading and insufficient for correct assessment of the treatment effect. For example, when treatment is given on worsening of the symptoms, patients receiving treatment will do worse than patients who do not, creating an appearance of treatment being harmful. We will build causal models to disentangle the learning effect of the patient history that contributed to the treatment decision from the benefit of treatment to the patient with the specific history. In doing so we will adopt the counterfactual causal inference approach. First we will construct a survival model for the time of initiation of the interventional procedure as a function of patient's history and baseline clinical characteristics. We assume no unmeasured confounding, meaning that treatment decisions are based only on the observed information. This analysis will deliver secondary results on current practices with interventional procedures. To link a treatment strategy to the expected outcome, we will use models for analgesic responses outlined above and in the Research Project. A joint model of symptom progression and its interaction with the treatment process will allow us to assess the benefit of treatment independent of a patient's symptom history.

Missing data. With high-dimensional phenotyping and the longitudinal character of the study missing data will be inevitable. Handling of missing data will include descriptive analysis of missing data patterns followed by the analysis of reasons for missingness as a nominal response using multinomial logistic regression. Sensitivity analyses will include missing data imputation by predictive-matching algorithms and missing data exclusion under a missing-at-random assumption. We do not expect more than 15% of missing data. If this assumption is not confirmed, multiple imputation approaches will be utilized.

Safety monitoring. Even though no serious side effects are expected from the treatments, in addition to the safeguards in the SMART trial of the Research Project, the Core will monitor safety periodically with 3 interim analyses and one final analysis, using the Fleming design (Fleming, T.R. (1982) One-Sample Multiple Testing Procedure for Phase II Clinical Trials, *Biometrics* 38, 143-151). The analysis will occur after each consecutive recruitment group of another 100 patients has completed their treatments (400 planned patients total under active treatments after drop-out).

Although it is highly unlikely that there will be extensive adverse events related to the study treatment that is any grade 2 or higher because these are all commonly used treatments for cLBP, we have established

an alarm procedure. The alarm procedure is designed to give early warning if the rate of any related AEs, grade 2 or reaches 15% or above. We will consider an alarm when more than 22, 32, 42, and 52 patients show adverse events and classify as related events and are a grade 2 or higher at the 3 interim tests and the final analysis, respectively. Events that may require the study to be discontinued or participant to be withdrawn from the study are described in Section 22.

Handling protocol deviations. Participant-specific protocol deviations will be assessed for their potential relationship to the treatment effects or the course of the disease by a medical expert. Since deviations because of safety will generally result in incomplete data on the subject, their consequences will be handled in the analysis as potentially informative missing data (as described above). Because of the difficulty of accurate determination of the relationship between protocol deviations and the treatment efficacy and the disease dynamics, several versions of the primary and secondary analysis will be undertaken:

Exclusion of the violators from the analysis population under the missing at random assumption.

1. Single (if, as expected, missing data fraction does not exceed 15%) or multiple imputation of the violator's unobserved responses using predictive matching algorithms, including the per-protocol analysis of the resultant imputed population(s).
2. With yes/no responses that have the meaning of success or failure where mixed logistic models are used per protocol, violator's responses will be classified as failures for the conservative analysis.
3. Analytic methods (2,3) applied only to violators classified as treatment or disease-related as defined by medical experts.

Power for explaining treatment effects. Consider a regression model correlating within-patient improvement due to one of the 4 main treatments with a phenotypic variable. Using a two-sided test for correlation at 5% significance level we conclude that we will have the power of at least 86% to detect correlation of 0.3 or higher, conservatively assuming the model is applied to one randomized treatment segment with 100 patients. This corresponds to first phase or second phase treatment in one of the 4 treatment groups, and a model based on the light phenotyping patient group of 400 total. Similar analysis for the smaller subgroup based on 40 patients with available deep phenotyping for a specific treatment and segment shows that correlation of 0.43 or higher will be detectable with 81% power. This is well within reach as evidenced by available literature on the association between treatment effects and phenotype variables. For example, mindfulness and pain responses showed correlations of 0.43-0.51 in prior reported studies. Our previous studies of the association between pain centralization and analgesic responses in knee OA showed similar or higher correlations.

Power for prediction. We expect that at least 30% of patients will show 50% improvements in analgesic outcomes under each of the treatments. We expect the predictive panel of light phenotypic variables to show AUC exceeding a clinically relevant AUC of 0.7, dependent on the specific setting. Under this assumption we will have the power of at least 91% to reject the null hypothesis AUC of 0.5 by a two-sided test in the subgroup analysis setting described above. With the panel including the deep phenotyping variables we expect to be able to reach a better AUC of 0.8 or higher. However, the analysis is based on smaller size of the subgroup (40 vs. 100). This results in the power of at least 89% for a similar test of AUC.

Go/no-go decisions to recommend model-based predictor panel for future clinical use. We are targeting a high sensitivity of the predictive panel of 80%. Under this scenario, the cross-validated ROC curve will be kernel-smoothed, and the decision threshold will be determined from the smoothed data to meet the 80% sensitivity. Under a normal approximation to the panel score distribution for patients who show 50% improvement and the ones who do not, in the hypothetical scenario of the above power calculation, we assess that the expected specificity value at 80% sensitivity will be around 50%. To provide guidance at the end of the study as to whether the panel is worth recommending for use in the clinical setting, worth a further study or non-promising, we will consider the overall rate of correct decisions. With the targeted sensitivity and specificity and the expected pain improvement rate in the subgroup, we are expecting that the decision will be at least 41%

correct overall. We will consider the assay not useful if it has the true overall correct decision rate of 25% or less. Dependent on the outcome, the panel will be potentially considered worth of further pursuit in the sense of potentially doubling the sample size in a future study and having a non-ambiguous decision at the end with Type I and type II errors of 5% each. Using the Fleming sequential testing design we conclude that with less than 13 correct predictions of improvement under treatment at the end of the current study the panel will be considered not worth pursuing. With 21 or more correct decisions, the biomarker will be considered clinically relevant, and with the number of correct decisions between 13 and 21, we will consider the biomarker worth of further study.

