### 8 Summary of Study Data

A CONSORT flow diagram (Appendix A) will compare how the study unfolded with the pre-trial plan to include information about the number screened, the number enrolled, the number randomized to each intervention at each stage of the trial, final completion rates, and the number of individuals in analytic datasets.

We will use descriptive statistics to assess data quality and characterize relationships between phenotype features prior to each treatment. In preparation for the main multivariate model-based

analysis we will look at correlations between phenotype variables and responses with correlation analysis and scatterplots, analyze data for evidence of collinearity between factors, study patterns of missing data, and conduct univariate analysis using models described below. The goal of the data summarization is to elicit a good feel for the specific data in our team of analysts and to guide an initial approach to data reduction and predictive model trimming.

At first, all intervention groups will be combined. Any variable that requires creation from collected data will be coded and created for examination. Continuous variables will be summarized by minimum, maximum, arithmetic mean, median, and standard deviation at each time point. Histograms and boxplots will be used to assess distributional characteristics of baseline and follow-up variables. The outcomes will be summarized and plotted at each time of assessment to assess distributional characteristics. Categorical variables will be tabulated with frequencies and percentages. The number and percentage of missing observations for all variables will be reported for each variable at each time point for the entire sample. Missingness for the primary and secondary outcome variables will be assessed by intervention group to evaluate any differential missingness.

We will then describe the patient population by initial intervention group to construct a table describing the baseline characteristics of each intervention group. The table will include baseline characteristics, baseline medical history, and baseline values of primary and secondary outcome variables. Significance testing of baseline characteristics between groups will not be performed based on statistical and CONSORT recommendations.

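### Protocol 18.1.5 and SAP 8 let phenotype-response correlations guide predictor trimming before cross-validation, with no rule to repeat the trimming inside the folds, so the cross-validated AUC would be optimistic by an uncertain amount

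*Protocol*

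**What the plan says.** Protocol 18.1.5 opens with a descriptive stage placed before the modelling: "In preparation for the main multivariate model-based analysis", the analysts write, "we will look at correlations between phenotype variables and responses with correlation analysis and scatterplots". The same sentence adds checks for collinearity, a study of missing-data patterns, and univariate analysis with the response models. The stated goal is to familiarise the analysts with the data and "to guide an initial approach to data reduction and predictive model trimming". SAP 8 carries the same text: "The goal of the data summarization is to elicit a good feel for the specific data in our team of analysts", followed by the same trimming purpose.

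The paragraph on best model selection then says the team will "use 10-fold cross-validation to protect against overfitting the model", and proposes elastic-net penalties, with LASSO preferred, for "potentially high-dimensional phenotype variables". Predictive performance is reported as cross-validated explained variation and a cross-validated AUC. Under power for prediction the protocol states "We expect the predictive panel of light phenotypic variables to show AUC exceeding a clinically relevant AUC of 0.7", and an AUC of 0.8 or more for the deep panel. Both are tested against 0.5. The go/no-go paragraph takes the panel's decision threshold, at 80% sensitivity, from the cross-validated ROC curve.

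Neither document says that trimming is repeated within folds, is done without sight of the response, or is checked on patients who played no part in it.

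**The concern.** Cross-validation gives an honest estimate only of the steps that are repeated within each training fold. If the response is used to decide which predictors enter the model, and that is done once on everyone, each held-out patient has already influenced the model that is later scored on that patient. Penalised fitting inside the folds cannot undo this, because the choice of inputs already carries the held-out responses.

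At stake are the quantities that rest on the cross-validated predictions: the AUC and its test against 0.5, the explained variation, and the 80%-sensitivity threshold. The protocol intends them to inform whether a panel is recommended for clinical use, studied further or dropped.

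**Working it through.** **Inputs from Protocol 18.1.5.** Responder rate 30%. Light panel: 100 patients per treatment (30 responders, 70 non-responders), expected AUC 0.7, stated power at least 91%. Deep panel: 40 patients (12 and 28), expected AUC 0.8, stated power at least 89%. The null AUC is 0.5, two-sided. The 5% level is stated for the correlation test and assumed here for the AUC test.

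**Step 1: reproduce the stated power.** Hanley-McNeil variance: Var(A) = [A(1−A) + (n1−1)(Q1−A²) + (n0−1)(Q2−A²)] / (n1·n0), with Q1 = A/(2−A) and Q2 = 2A²/(1+A). Power = Φ[(A − 0.5 − 1.96·SE0)/SE1], where SE0 is taken at A = 0.5 and SE1 at the expected AUC.

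- Light: SE1 = √[(0.21 + 29×0.0485 + 69×0.0865)/2100] = 0.0601. SE0 = √[(0.25 + 98/12)/2100] = 0.0633. Power = Φ[(0.2 − 0.1241)/0.0601] = 0.897. Using SE1 throughout gives 0.914, the Obuchowski variance 0.907, and a simulated Mann-Whitney test 0.911.
- Deep: SE1 = √[(0.16 + 11×0.0267 + 27×0.0711)/336] = 0.0840. SE0 = √[(0.25 + 38/12)/336] = 0.1008. Power = Φ[(0.3 − 0.1976)/0.0840] = 0.888. Obuchowski gives 0.893 and the simulation 0.897.

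The stated figures reproduce. The same null standard errors imply that the test rejects 0.5 once the AUC passes 0.5 + 1.96×0.0633 = 0.624 (light) or 0.5 + 1.96×0.1008 = 0.698 (deep).

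**Step 2: trimming on pure noise.** Assumptions: normal predictors unrelated to the response; the top 30% of the response labelled responders; predictors with the strongest correlation with response kept; linear discriminant with a small ridge; stratified 10-fold cross-validation; pooled AUC; 300 to 600 trials per setting. The numbers of candidates and kept predictors are assumptions. The documents fix neither, although the SAP names 8 light interactions and 15 deep predictors, and the protocol's graph analysis uses 264 nodes.

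Screening once on all patients, continuous response, independent predictors:

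| Panel | Candidates → kept | Mean AUC | Reaches expected AUC |
|---|---|---|---|
| Light | 8 → 5 | 0.522 | 0.5% |
| Light | 20 → 10 | 0.569 | 4% |
| Light | 50 → 10 | 0.642 | 21% |
| Light | 100 → 10 | 0.680 | 38% |
| Light | 500 → 10 | 0.746 | 81% |
| Deep | 15 → 5 | 0.594 | 3% |
| Deep | 50 → 5 | 0.680 | 11% |
| Deep | 100 → 5 | 0.724 | 24% |
| Deep | 264 → 5 | 0.760 | 33% |

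Variations for the light panel:

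- Continuous screening, predictors correlated at 0.3, 60 to 100 candidates, 10 kept: 0.59 to 0.61, reaching 0.7 in 10% to 16%.
- Continuous screening, independent, 60 candidates, 30 kept: 0.60 and 6%.
- Screening on responder status, independent, 60 candidates, 10 kept: 0.73 and 75%.

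**Step 3: the same screening inside each training fold.** Mean AUC is 0.48 to 0.50 in every setting. The expected AUC is reached in 0.3% to 2.0% of light-panel trials and 0.2% to 3.0% of deep-panel trials.

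Comparing Steps 1 and 2: with 50 independent light candidates, the mean noise AUC (0.642) already lies above the rejection point (0.624). With 100 deep candidates it does too (0.724 against 0.698).

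**The case against.** The strongest reply is that the text describes exploration and sets no filter. The response correlations sit beside collinearity and missingness checks, which could drive the trimming alone. The verb is only to guide, no keep-or-drop rule is given, and feature elimination is assigned to LASSO. This stands in part: screening on the full data outside the folds is inferred from the order of steps and the absence of a nesting rule, and a reader who takes it as stated outright goes too far. But the response-based work has trimming as a named purpose, and informal trimming leaks information just as a formal filter does.

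Second, the SAP's own models are largely clear of the problem. Objective 1 tests pre-specified modifiers. Objective 2 describes univariate summaries, Spearman checks for collinearity and an adaptive elastic net, with no response-based filter. The SAP sets out no AUC or go/no-go analysis. All of this stands, so a reader should not infer that the Objective 1 tests are compromised.

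Third, a reader might infer that the ROC curve fixes the go/no-go boundaries, or that SAP 7.5 substitutes cross-validation for multiplicity control. Neither is supported. The boundaries are counts of correct predictions (13 and 21), which these simulations did not evaluate. SAP 7.5 justifies the absence of adjustment by the trial's aim and low power, and adds cross-validation as a further check where appropriate.

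Fourth, Protocol 18.1 is headed as exploratory. That lowers the stakes, but the section still uses the result to decide whether a panel should be recommended.

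**Conclusion.** The point holds as a gap with a predictable direction. Followed in the order written, the protocol's cross-validated AUC, explained variation and 80%-sensitivity threshold would be biased upward. The size is uncertain. It is negligible with about 8 candidates. With 20 to 100 independent candidates screened on the continuous response, the light-panel target of 0.7 is reached on noise in 4% to 38% of trials. It is larger with binary screening or very many candidates, and smaller when predictors are correlated or more are kept.

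A reader might infer that the targets would routinely be met on noise. The documents do not support that: it needs binary screening, very large candidate pools or severe trimming, none of which they specify. The continuous response is the protocol's primary line.

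**What to change.** State in Protocol 18.1.5 and SAP 8 that full-data descriptive work used for trimming is limited to predictor-only checks (missingness, distributions, collinearity). State also that any screening or trimming that uses the response is redone within each training fold, so that the reported AUC and explained variation cover the whole pipeline. Response plots and correlations may still be reported, provided they do not decide which predictors enter.

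The cost is a sentence or two in each document, slightly more computing, and lower reported AUCs. Trimming by judgement would have to be written as a rule so that it can be repeated in each fold.
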